## Research Question/Hypothesis

- Research Question: Will preterm neonates with estimated gestational age of 26 0/7 to 32 6/7 gestation who are supplemented with iron on an every-other-day (EOD) dosing, compared to those who are supplemented with iron daily, have the same incidence of achieving iron replete status (reticulocyte-Hb >29) at 36 weeks post-menstrual age (PMA)?
- Hypothesis: We hypothesize that at the same dosage in oral form, there will be no difference in the incidence of preterm neonates achieving iron replete status as measured by reticulocyte hemoglobin (Ret-Hb) between EOD and daily iron supplementation.

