## Objectives

- Primary objective: determine if daily versus EOD oral iron at the same dose per kilogram per day will achieve similar incidence of iron replete status at 36 weeks PMA.
- Secondary objective:
  - Characterize Ret-Hb levels in preterm infants
  - Identify the number of blood transfusions received between enrollment and 36 weeks' PMA between two groups
  - Determine prevalence of bronchopulmonary dysplasia between two groups
  - Identify the number with sepsis (defined as a positive blood or cerebrospinal fluid culture that was treated with antibiotics for at least 7 days) between two groups
  - Identify the number with necrotizing enterocolitis (NEC)/gastrointestinal perforation (medical NEC defined as  $\geq$ stage II Bell's criteria between two groups
  - Characterize growth (assessed by length gain at 36 weeks' PMA or at discharge if discharged before 36 weeks) between two groups

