## METHODOLOGY

### Study design

- This is a non-inferiority, blinded, randomized control trial designed to investigate if EOD iron is comparable to daily iron dosing in achieving iron replete status by Ret-Hb measurements in premature infants.

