### Intervention

- The control group / current standard for iron supplementation in neonates is detailed as follows: after the infant achieves full enteral feeds, the infant is started on 6 mg/kg of oral iron daily supplementation. Though the American Academy of Pediatrics and World Health Recommendation recommend 2 – 4 mg/kg of supplemental iron for premature infants, studies examining the effects of higher dose of enteral iron supplementation (3.4 mg/kg to 7.1 mg/kg per day) revealed no differences between the lower versus higher dosages on morbidity (sepsis, necrotizing enterocolitis, or enteral feeding intolerance) and mortality outcomes. The dose of 6 mg/kg of enteral iron was chosen based on the aforementioned recommendations with evidence of its safety, while minimizing the need to increase the enteral iron dosage if an infant were to be started on ESAs where a dose of 6 mg/kg of enteral iron supplementation is the standard practice. Phlebotomy to obtain a complete blood count, reticulocyte count, and reticulocyte hemoglobin count is pursued the Monday after iron supplementation is started and every 2 weeks thereafter to monitor hematocrit or hemoglobin levels and iron status.

- The intervention group for EOD iron supplementation in neonates is as follows: after the infant achieves full enteral feeds, the infant is started on 6mg/kg of oral iron supplementation administered every other day. Phlebotomy to obtain a complete blood count, reticulocyte count, and reticulocyte hemoglobin count is pursued the Monday after starting iron supplementation and every 2 weeks thereafter to monitor hematocrit or hemoglobin levels and iron status. There is literature revealing that neonates even <29 weeks' gestation absorb and regulate iron similar to adults. There is literature revealing that there is no difference between EOD and daily iron supplementation in older pediatric populations and adults in improving hemoglobin levels, with one study in Switzerland revealing that EOD iron reduced iron deficiency in the longer term and triggered fewer gastrointestinal side effects in adult women. Given the evidence that premature infants regulate their iron status similarly to older infants and adults, and the current evidence of EOD iron in older children and adults, this intervention, compared with our control, will help us address our primary question to determine if EOD iron is non-inferior to daily iron.

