## Data Analysis

- A sample size determination was conducted using Riskcalc.org (Chow S-C, Shao J, Wang H, Lokhnygina Y. Sample Size Calculations in Clinical Research. Third ed: Chapman and Hall/CRC; 2017.) and confirmed by [name] (BAMC Statistician). Sample size estimates are for type 1 error of 5% ( $\alpha = 0.05$ ), power ( $1-\beta$ ) of 80%, ratio of 1:1 of intervention to control. The effect size is determined by estimating the proportion of infants with Ret-Hgb >29 pg to be similar at 80% between daily versus EOD iron, with a margin of 20%. It was determined that a sample size of 100 patients would be needed for this study (50 for intervention, and 50 for control).
- A statistician who is blinded to the study allocation will analyze the data. All statistical analyses will be performed with IBM SPSS Statistics (Armonk, NY: IBM Corp) and JASP Team (2022). JASP, Version 0.16.1 (Netherlands: JASP Team). Descriptive statistics will be performed for all variables. Categorical data will be reported as percentages, and continuous data will be reported as medians with interquartile range or means with standard deviation. The two groups will be compared according to the intention to treat with the use of Student's t-tests, Mann-Whitney-U tests, chi-square analysis based on the outcome being evaluated. All p-values will be one-sided, with a statistical significance level of <0.05. Covariates to include gestational age, in-born versus out-born infants, ESA use, receipt of pRBC transfusion will be controlled for using a logistic regression model and will be reported with an odds ratio (OR) and 95% confidence intervals (CI). A medical monitor who is not involved in the study will be assigned prior to the initial enrollment of the trial to monitor the data periodically (every 3 months) to ensure the safety of the participants and the scientific integrity of the study. An interim analysis will be performed at halfway to target enrollment.

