### **Benefits of Proposed Research to the Subjects and Others (significance of your study)**

- This will give us insight if EOD iron is equivalent to daily iron supplements. This may also benefit hospital costs as it can help reduce total iron utilization for the duration of the neonate's hospitalization. This study may also help researchers and clinicians gain insight if EOD iron is as efficacious as daily iron in achieving iron replete status in premature infants with the potential of minimizing the side effects of oral iron intake. Participants will not receive compensation for participating in this trial.

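### The formal hypothesis is no difference, but the trial is designed and sized for one-sided non-inferiority, so a pass cannot support no difference or equivalence

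*Protocol*

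**What the plan says.** The Protocol states its primary question in two ways.

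**As sameness.** The Research Question asks whether the two schedules give the same incidence of iron repletion at 36 weeks post-menstrual age, and the hypothesis beneath it is that "there will be no difference in the incidence of preterm neonates achieving iron replete status". The primary objective (Objectives) is to determine whether the schedules "will achieve similar incidence of iron replete status at 36 weeks PMA". The Benefits section says: "This will give us insight if EOD iron is equivalent to daily iron supplements".

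**As non-inferiority.** Study design: "This is a non-inferiority, blinded, randomized control trial". The Intervention section says the comparison will help "address our primary question to determine if EOD iron is non-inferior to daily iron".

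The Data Analysis section gives the operating figures: "Sample size estimates are for type 1 error of 5" percent, 80% power, 1:1 allocation, 80% replete assumed in both arms, and a margin of 20%. "It was determined that a sample size of 100 patients would be needed for this study", that is 50 per arm. On sidedness: "All p-values will be one-sided, with a statistical significance level of <0.05".

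The margin is given without a direction. Nowhere does the Protocol write a null hypothesis at the margin, and nowhere does it give an upper limit, a symmetric margin or an equivalence test.

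**The concern.** A claim of no difference, or of equivalence, needs a limit in both directions. Non-inferiority needs one in the unfavourable direction only. The hypothesis section is where a reader looks to learn what a positive result will mean, and here it names a conclusion that the declared design cannot deliver.

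What is at stake is the wording of the primary conclusion. If the analysis passes at the 20-point margin and is read against the hypothesis as written, the trial could be described as having shown that the schedules do not differ, when it has only excluded a deficit of 20 points or more. The Protocol's own Background links iron deficiency in infancy to impaired neurodevelopment, so the difference between those two statements matters to those who use the result.

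**Working it through.** **Inputs, all from Data Analysis:** repletion 80% in both arms (true difference 0); margin 20%, read as percentage points, the reading under which the stated figure reproduces; alpha 0.05, one-sided; power 80%; 50 per arm. No dropout allowance is stated, so every power below assumes 50 evaluable infants per arm.

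**Step 1: reproduce the Protocol's sample size.** Variance term: 2 x 0.8 x 0.2 = 0.32. Margin squared: 0.20^2 = 0.04.

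- Non-inferiority, one-sided 5%: n = (1.645 + 0.842)^2 x 0.32 / 0.04 = 49.46, so 50 per arm. This matches.
- Non-inferiority, one-sided 2.5%: 63 per arm. No match.
- Equivalence by two one-sided 5% tests: n = (1.645 + 1.282)^2 x 0.32 / 0.04 = 68.5, so 69 per arm. No match.

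Of these, only one-sided 5% non-inferiority gives the stated figure.

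**Step 2: power of the declared design.** SE = sqrt(0.32 / 50) = 0.08, and margin / SE = 0.20 / 0.08 = 2.5. Power = Phi(2.5 - 1.645) = 0.804. Exact binomial enumeration with Wald limits gives 81.3%. The stated 80% is correct for non-inferiority.

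**Step 3: what a pass establishes.** The test rejects p(EOD) - p(daily) <= -0.20 when the lower confidence limit lies above -0.20. No condition is placed on the upper limit. The conclusion is that EOD iron is not worse by 20 points or more, and nothing further.

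**Step 4: illustration only, equivalence at the same size.** Suppose equivalence meant within 20 points in either direction. At 50 per arm and a true difference of zero:

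- 5% per side: 2 x Phi(2.5 - 1.645) - 1 = 2 x 0.8038 - 1 = 0.608 (exact enumeration 62.5%).
- 2.5% per side: 2 x Phi(2.5 - 1.960) - 1 = 2 x 0.7054 - 1 = 0.411 (exact enumeration 42.8%).

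Reaching 80% would take 69 or 85 per arm respectively. Both the symmetric margin and the level per side are assumptions made here. A literal zero difference cannot be demonstrated at any sample size.

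**Step 5: how much one passing result proves.** Take 37/50 (74%) on EOD iron and 40/50 (80%) on daily iron. The difference is -0.06, with SE = sqrt((0.74 x 0.26 + 0.80 x 0.20) / 50) = sqrt(0.3524 / 50) = 0.0840. The limits are -0.06 -/+ 1.645 x 0.0840, or about -19.8 to +7.8 points. This passes non-inferiority while remaining compatible with a deficit of almost 20 points, so it would not justify a statement of no difference. It would also fall inside a +/-20 point equivalence range, so it does not separate non-inferiority from equivalence. When the lower limit already clears -20, the two designs part only where the upper limit exceeds +20 points.

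**The case against.** The best defence is that the operative sections agree with one another. Study design declares non-inferiority, Intervention restates the primary question as non-inferiority, and Data Analysis supplies a margin, one-sided p-values and a sample size that fits that design. On this view the hypothesis sentence merely records what the investigators expect to be true, namely equal rates, which is the assumption behind the power calculation. The Benefits sentence is lay language and conditional, and words such as similar or as efficacious are not strictly two-sided.

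Much of this stands. The design and its sizing are coherent, the Benefits section announces no conclusion, and the softer words alone would not be worth raising. But the sentence in question stands as the trial's formal hypothesis, not as a planning assumption, and no null hypothesis at the margin appears elsewhere to override it. A statistical analysis plan may exist and may write that null out. It would still be implementing a Protocol that states two different primary questions.

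A reader might go further and infer that the trial is underpowered, with about 61% power rather than 80%. The documents do not support that: 61% belongs to an equivalence test that the Protocol never proposes, and it moves to 41% with a different assumption about the level per side. A reader might also infer that the investigators intend to report a pass as equivalence. No section sets such a reporting rule.

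**Conclusion.** The contradiction is real and lies in the wording of the hypothesis, not in the arithmetic. Fifty per arm and 80% power are right for one-sided 5% non-inferiority (49.46 per arm; 80.4% power), given 80% replete in both arms, a 20-point margin and 100 evaluable infants. The hypothesis as written is not the one that this design tests. A pass excludes a deficit of 20 points or more on EOD iron and supports neither no difference nor equivalence. The equivalence powers of 61% and 41% only illustrate the gap and are not properties of this trial. The point should be corrected, because it governs what the trial may conclude and is cheap to put right.

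**What to change.** In Research Question/Hypothesis, state H0: p(EOD) - p(daily) <= -0.20 against H1: p(EOD) - p(daily) > -0.20, where p is the proportion iron replete at 36 weeks post-menstrual age. Reword the research question and the primary objective to match, and replace the reference to equivalence in the Benefits section. State that the primary conclusion on a pass is limited to EOD iron being not worse than daily iron by 20 percentage points or more.

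Relabelling the trial as equivalence at its present size is not recommended: on the illustrative assumptions above it would turn an adequately sized non-inferiority trial into an underpowered equivalence trial.

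The cost is a protocol wording change and a slightly less favourable claim. Sample size, margin and alpha are unchanged.

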## Objectives

- Primary objective: determine if daily versus EOD oral iron at the same dose per kilogram per day will achieve similar incidence of iron replete status at 36 weeks PMA.
- Secondary objective:
  - Characterize Ret-Hb levels in preterm infants
  - Identify the number of blood transfusions received between enrollment and 36 weeks' PMA between two groups
  - Determine prevalence of bronchopulmonary dysplasia between two groups
  - Identify the number with sepsis (defined as a positive blood or cerebrospinal fluid culture that was treated with antibiotics for at least 7 days) between two groups
  - Identify the number with necrotizing enterocolitis (NEC)/gastrointestinal perforation (medical NEC defined as  $\geq$ stage II Bell's criteria between two groups
  - Characterize growth (assessed by length gain at 36 weeks' PMA or at discharge if discharged before 36 weeks) between two groups

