- In older populations, EOD iron supplementation is as effective as daily iron supplementation in the treatment of iron deficiency anemia, with studies revealing significantly fewer gastrointestinal side effects in those who are on EOD iron. Adults regulate their iron status through a feedback pathway involving hepcidin whereby iron-sufficient individuals will have upregulated hepcidin, which leads to decreased iron absorption and availability. Recent studies have revealed that pediatric patients and premature neonates regulate iron absorption through hepcidin in a similar fashion. A randomized control trial in Kenya found that consecutive day iron dosing increases hepcidin and decreases iron absorption, compared with EOD dosing in pediatric patients as young as 5 months of age. Though the regulation of iron status through hepcidin has been studied in extremely premature neonates, the clinical effect of EOD dosing of iron has not yet been examined in this population.

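### The primary objective claims equal iron per kilogram per day, but the two regimens differ two-fold on that basis (nominally 6 versus 3 mg/kg/day)

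*Protocol*

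**What the plan says.** The primary objective (Protocol, Objectives), assessed at 36 weeks PMA, is to "determine if daily versus EOD oral iron at the same dose per kilogram per day will achieve similar incidence of iron replete status". It therefore fixes the dose basis of the comparison as equal per kilogram per day.

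The Intervention section then defines the arms. For control, "the infant is started on 6 mg/kg of oral iron daily supplementation". For the intervention arm, "the infant is started on 6mg/kg of oral iron supplementation administered every other day".

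Three other places bear on the point:

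- The hypothesis (Research Question/Hypothesis) begins "We hypothesize that at the same dosage in oral form" and gives no time unit. The research question just above it compares infants "who are supplemented with iron on an every-other-day (EOD) dosing, compared to those who are supplemented with iron daily" and sets no dose condition.
- Background to Research Questions supports alternate-day dosing partly by a schedule effect, reporting a trial in which "consecutive day iron dosing increases hepcidin and decreases iron absorption, compared with EOD dosing".
- The section on the benefits of the research expects of every-other-day iron that "it can help reduce total iron utilization for the duration of the neonate's hospitalization".

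**The concern.** The objective attributes to the comparison a property, equal daily iron, that the regimens do not have. This matters because the dose basis decides what the primary result can be said to show.

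At equal mg/kg/day, the only difference between the arms would be the spacing of doses, and the result would bear directly on the hepcidin argument in the Background. Under the Intervention section, spacing and cumulative iron change together, and two arms cannot separate them. A non-inferior result could mean that better absorption on alternate days offsets the smaller total, or that the smaller total is enough on any schedule. An inferior result could come from the schedule or from the lower total. A report written to the stated objective would credit either result to the schedule.

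The protocol also carries two dose bases at once, so a reader of the Objectives and a reader of the Intervention section would not describe the every-other-day arm in the same way.

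**Working it through.** **Inputs**

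| Item | Value | Source in Protocol |
|---|---|---|
| Dose basis claimed | equal mg/kg per day | Objectives |
| Control regimen | 6 mg/kg, every 1 day | Intervention |
| Every-other-day regimen | 6 mg/kg, every 2 days | Intervention |
| Interval for the cumulative check | 14 days, from "every 2 weeks thereafter to monitor hematocrit or hemoglobin levels and iron status" | Intervention |

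**Nominal average daily dose** = dose per administration ÷ dosing interval in days.

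- Daily arm: 6 ÷ 1 = 6 mg/kg/day
- Every-other-day arm: 6 ÷ 2 = 3 mg/kg/day
- Ratio: 3 ÷ 6 = 0.5

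**Cumulative dose over one monitoring interval** = number of administrations × dose per administration.

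- Daily arm: 14 × 6 = 84 mg/kg
- Every-other-day arm: 7 × 6 = 42 mg/kg
- Ratio: 42 ÷ 84 = 0.5

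Over 28 days the figures are 168 and 84 mg/kg, with the same ratio. Over an odd number of days that starts with a dose, the gap is slightly smaller: in 7 days, 7 × 6 = 42 against 4 × 6 = 24 mg/kg, a ratio of 24 ÷ 42 = 0.57. The two-fold figure is therefore a nominal average.

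**Can the text be read so that the conflict disappears?** Only if the daily basis in the objective means the amount given on a day when iron is given. The protocol does not say so, and two places point the other way:

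- When the Intervention section justifies the dose, it cites earlier studies of 3.4 to 7.1 mg/kg per day, using the unit as an ordinary daily rate. On that scale the arms are 6 and 3.
- At equal mg/kg/day, total iron given would not fall. The saving expected in the benefits section follows from the regimens and contradicts the objective.

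The hypothesis is compatible with equality per administration but names no time basis, so it does not settle the question.

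**Does the sample size depend on this?** The Data Analysis inputs are 80% in both arms, a margin of 20 percentage points, one-sided 5% and 80% power:

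n per arm = 2 × 0.8 × 0.2 × (1.645 + 0.842)² ÷ 0.20² = 0.32 × 6.18 ÷ 0.04 ≈ 49.5, rounded up to 50.

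This reproduces the stated 50 per arm (100 in total). Dose is not an input, so the number does not change.

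**The case against.** The strongest reply is that one loose phrase stands against the rest of the protocol. The Intervention section states both regimens without ambiguity and ties them to the primary question. The research question and the study design section ask about every-other-day against daily iron with no equal-daily-dose condition, and the benefits section expects less iron to be used. On this view the phrase was probably meant as the amount per dosing day, and the harm depends on how a future report is worded. Moreover, if more iron does not lower reticulocyte hemoglobin, halving the cumulative iron works against the every-other-day arm, so it does not make a false claim of non-inferiority easier.

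Much of this stands. The regimens are explicit, the design can answer a comparison of the two regimens as given, and the validity of the test is not at issue. The hypothesis is imprecise rather than contradictory, so aligning it, like writing out the daily averages, is a minor addition.

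The reply does not remove the contradiction. The phrase sits in the primary objective, the sentence against which the result will be reported, and the benign reading is nowhere written. Circumstantial support for the regimens is not a statement of which text was intended. A problem that affects the label on the result and not its validity is still worth correcting when that label is the trial's primary claim.

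**Conclusion.** The concern holds. The primary objective and the Intervention section contradict each other by a factor of two on the basis that the objective calls equal: nominally 6 against 3 mg/kg/day, or 84 against 42 mg/kg per 14 days. The cumulative figures assume that every administration stays at the stated 6 mg/kg through the interval; no assumption is needed about when full feeds are reached.

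The consequence is limited to the stated objective, the hypothesis and the conclusion drawn from them. As the arms are written, the result applies to two regimens that differ in both schedule and cumulative iron, not to schedule at equal daily iron. It should be fixed, and it does not invalidate the design. No view is taken here on which dose or section is right.

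**What to change.** Reconcile Research Question/Hypothesis, Objectives and Intervention so that one explicit dose basis, per administration or per day, governs the objective, hypothesis and conclusion. State each arm's nominal average mg/kg/day. Which text is kept is for the investigators.

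- **If the Intervention regimens stand:** describe the objective and conclusion as a comparison of two regimens that differ in schedule and cumulative iron, and do not report a positive result as non-inferiority at equal mg/kg/day. The cost is a wording amendment to the objective and hypothesis, plus one line in the Intervention section.
- **If the objective is what was intended:** the Intervention section does not deliver it. The regimens and the statement on total iron use in the benefits section would have to be revisited, which is more than wording.

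The dose wording itself calls for no change to the sample size calculation.

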- Phlebotomy to obtain a complete blood count, reticulocyte count, and reticulocyte hemoglobin count may be pursued sooner than the 2-week mark based on physician judgment and the clinical status of the infant.
- Parents or guardians of infants who meet inclusion criteria will be consented prior to enrollment into the study. Following written informed consent, eligible participants will be randomized by simple randomization to the EOD arm or daily arm by computer generated sequence of random numbers. Allocation will be concealed using sequentially numbered opaque sealed envelopes which will be unknown to the investigators. The random sequence will be generated by a statistician who will not be directly involved in the care of patients.
- All study-related materials will be destroyed after official closure has been confirmed by the IRB.

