### **Study Subjects**

- The population to be studied include premature infants who completed 26 0/7 to 32 6/7 weeks' gestation. We will include premature infants who are on full enteral feeds and are started on oral iron

therapy. Infants with known congenital anomalies or chromosomal abnormalities (such as Trisomy 18 or Trisomy 21), conditions that affect iron metabolism (such as thalassemia or hemochromatosis), bleeding disorders or coagulopathy, and received iron parenterally will be excluded from the study.

- There will be need for a written consent from the patient's' parent or legal guardian. A copy of the written consent will be included in the appendix.
- Our target population are neonates, which fall under the category of special subject population. Literature on the benefits of every other day iron dosing compared with daily iron dosing is already available in older pediatric patients and adults. There have been no studies investigating their benefits in the neonatal population, despite this population being the most vulnerable to iron deficiency and its consequences, as well as emerging evidence that neonate regular iron metabolism similar to adults.

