### **Data Collection**

- The electronic medical records of CHRISTUS and Brooke Army Medical Center (BAMC) will be queried for patients who meet inclusion criteria as described above and consented for participation in the trial. Patient demographic information will be collected, along with other variables as outlined below:
  - Maternal Information
    - Age
    - Race / ethnicity: non-Hispanic White, non-Hispanic Black, Hispanic, Asian/Pacific Islander, Native
    - For patients at BAMC:
      - Mother Active Duty, Non-Active Duty, Retired
      - Rank of Active Duty: Enlisted versus Officer
    - Past medical history such as anemia, diabetes, mood disorder, hypertension, and more
    - Prenatal laboratory history: result of hepatitis B, syphilis, HIV, GBS status, blood type, rubella and varicella immunity status, gonorrhea and chlamydia status
    - Medication history to include use of antidepressants, anticonvulsants, insulin, aspirin, iron supplementation
    - Complications during delivery such as postpartum hemorrhage (>500 mL vaginal delivery, >1000mL c-section), magnesium around labor/delivery time-period, required pRBC transfusion
    - Blood type, antibody status

- Hemoglobin, hematocrit results prior to delivery
- Neonatal Information
  - Gestational age at birth
  - Birth order (first born, not first born)
  - Weight at birth
  - Delivery method: vaginal versus cesarean section
  - Instrumentation at delivery: vacuum assisted, forceps assisted, none
  - Race / ethnicity: non-Hispanic White, non-Hispanic Black, Hispanic, Other, Asian/Pacific Islander, Native
  - Phototherapy requirement
  - Blood type, DAT status
  - Delayed cord clamping
  - Hemoglobin, hematocrit, mean corpuscular volume at:
    - T0= first lab draw following starting iron
    - T1 = 2 weeks following T0
    - T#= every 2 week intervals until 36 weeks PMA or discharge
  - reticulocyte count, reticulocyte hemoglobin at:
    - T0= first lab draw following starting iron
    - T1 = 2 weeks following T0
    - T#= every 2 week intervals until 36 weeks PMA or discharge
  - Change in hematocrit, hemoglobin, retic count, retic hemoglobin between end of trial and T0
  - Ferritin, Serum TIBC, and iron levels at 36 weeks PMA
  - Darbepoetin / EPO use
  - Number of pRBC transfusions

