  - Neonatal morbidities documented in the EMR which includes include anemia defined by unit guidelines based on the neonate's clinical status and corrected gestational age, necrotizing enterocolitis, sepsis, chronic lung disease, intubation, death, feeding difficulties
  - Neonatal severity scoring (NSOFA) at start of trial (T0) and every 2 weeks thereafter (T#)
  - Type of feed and calories from T0 to T#
  - Feeding volume at T0 to T#
  - Weekly growth parameters T0 to T# (weight, length, and head circumference)
  - Type of respiratory support T0 to T#
  - Blood draw volume T0 to T#
  - Transfusions from T0 to T#
  - Presence of specific diagnosis: constipation, feeding intolerance, infectious screen, clinical sepsis
- Data collected will include MRN; however, this will not be used in the analysis. All data will be deidentified before they are entered into REDCap for effective safeguard of information. Personnel

identified in this protocol will be responsible for collecting the data and will be the only persons who will have access to the de-identified data inputted on REDCap for further management and analysis.

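### For BPD, the only covariate list omits respiratory support before randomisation and includes ESA use and transfusion, which can follow randomisation; the cost is precision, not bias

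*Protocol*

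**What the plan says.** - **Outcome.** The Objectives section of the protocol lists, among the secondary objectives, "Determine prevalence of bronchopulmonary dysplasia between two groups". That line gives neither a definition nor a time of assessment. Another secondary objective is the number of transfusions between enrolment and 36 weeks' PMA.
- **Allocation.** Under Intervention, infants are "randomized by simple randomization to the EOD arm or daily arm by computer generated sequence of random numbers". No stratification is stated. Data Analysis sets 50 infants per arm.
- **Analysis.** Data Analysis allows t-tests, Mann-Whitney tests or chi-square according to the outcome, and adds one model: "Covariates to include gestational age, in-born versus out-born infants, ESA use, receipt of pRBC transfusion will be controlled for using a logistic regression model". It does not say which outcomes that model covers.
- **Respiratory data.** Data Collection includes "Type of respiratory support T0 to T" (the T-numbered visits every two weeks).
- **Timing of T0.** The same section defines "T0= first lab draw following starting iron". Intervention places that draw on the Monday after supplementation starts. The severity-score line in Data Collection, however, treats T0 as the start of the trial.

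**The concern.** Infants join the trial only once they are on full enteral feeds and starting oral iron, so some lung disease may already be established. Respiratory support at that point is likely to predict BPD strongly. With simple randomisation of 100 infants, the arms may differ in it by chance, and the one covariate list has no term for it. If the arms do differ, part of any observed BPD difference reflects who was already on support and not the iron schedule.

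The list also names ESA use and pRBC transfusion without limiting them to the time before randomisation. Transfusion after enrolment is itself one of the trial's outcomes. Adjusting BPD for something that the iron schedule may affect changes the question being answered and can introduce bias of its own.

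**Working it through.** **1. The plan's own figure.** The protocol gives no calculation for BPD. Its sample size is for the primary outcome: 80% in both arms, margin 20 points, one-sided 5%, power 80%.

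n per arm = 2 × 0.8 × 0.2 × (1.645 + 0.842)² / 0.20² = 49.5, rounded up to 50, so 100 in total. This reproduces. Nothing below changes it.

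**2. Chance imbalance in support.** Inputs: 50 per arm (Data Analysis) and a share s on support at entry (assumed; the protocol gives none).

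SD = √(2 × s × (1 − s) / 50). With s = 0.3: √(2 × 0.3 × 0.7 / 50) = 0.092, about 9 points.

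**3. Gain against no adjustment.** With assumed BPD risks p1 (supported) and p0 (not supported), and overall risk p = s·p1 + (1 − s)·p0:

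R² = (p1 − p0)² × s × (1 − s) / [p(1 − p)]; equivalent sample-size factor = 1 / (1 − R²).

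| s | p1 / p0 | p | R² | Factor |
|---|---|---|---|---|
| 0.2 | 0.40 / 0.10 | 0.160 | 0.107 | 1.12 |
| 0.3 | 0.60 / 0.10 | 0.250 | 0.28 | 1.39 |
| 0.3 | 0.70 / 0.05 | 0.245 | 0.48 | 1.92 |

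**4. Simulation.** 100 infants, simple 1:1 allocation, no treatment effect, 20,000 trials per scenario. The standard errors (SE) are for the BPD risk difference, in points: unadjusted √(4p(1 − p)/100), adjusted the same multiplied by √(1 − R²).

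| s | p1 / p0 | R² | SE unadjusted | SE adjusted | One-sided type I error, unadjusted |
|---|---|---|---|---|---|
| 0.3 | 0.40 / 0.10 | 0.12 | 7.8 | 7.3 | 5.0% |
| 0.4 | 0.50 / 0.05 | 0.27 | 8.4 | 7.2 | 5.1% |
| 0.5 | 0.60 / 0.05 | 0.34 | 9.4 | 7.6 | 5.4% |
| 0.4 | 0.70 / 0.05 | 0.47 | 9.2 | 6.7 | 5.1% |

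The mean BPD difference was about zero throughout. Imbalance in support exceeded 10 points in 28 to 32% of trials and 20 points in 3 to 5%. A given arm had at least 15 points more support in 5 to 7% of trials. In those trials the unadjusted BPD difference shifted by 5 to 12 points, and the one-sided error in that direction was 16 to 34%.

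**5. Gain beyond gestational age.** Gestational age is already listed, so the relevant gain over the listed model is what support adds to it. In an illustrative model in which gestational age drives both support and BPD, with all coefficients assumed, the factor is (1 − R² for age) / (1 − R² for both):

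- R² 0.179 to 0.205: 0.821 / 0.795 = 1.03
- R² 0.207 to 0.262: 0.793 / 0.738 = 1.07 to 1.08
- R² 0.317 to 0.402: 0.683 / 0.598 = 1.14

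Rounding R² to two decimals first gives 1.04, 1.07 and 1.13. Either way the gain is small. These factors are linear-model approximations on the risk-difference scale.

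**The case against.** The strongest reply is that nothing here is invalid. Randomisation already allows for chance imbalance: the unadjusted difference averages zero and its error rate is close to nominal. BPD is an unpowered secondary outcome, the covariate sentence is not clearly exhaustive, and outcome-specific covariates could be settled in an analysis plan that is not shown. Gestational age, which is listed, captures much of what support would add.

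Most of that stands, and it limits the point to precision. It does not answer two things. First, the protocol has already named covariates, and a later plan that repeats the list would carry ESA use and transfusion into the BPD model. Second, if BPD is compared by chi-square alone, which the text also allows, gestational age gives no help and the larger gains apply.

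A reader might infer that existing lung disease dominates the BPD comparison. The figures do not support that: support explains under half of the variance in every scenario tried, and those scenarios rest on assumed risks. Nor do the documents give the age at full feeds or say how far BPD is settled by then.

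A reader might also take the T0 record as the baseline value. By its definition in Data Collection, T0 follows the start of iron, so it is not a safe pre-randomisation covariate.

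**Conclusion.** The point holds as a minor one. The listed covariates suit BPD poorly: a likely strong predictor is absent, and two terms that can arise after randomisation are present, one of them overlapping a secondary outcome. The unadjusted comparison is unbiased.

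The cost is precision and exposure to imbalance with an SD of about 9 points if 30% are on support. The equivalent sample-size gain is about 1.1 to 1.9 against a raw chi-square, but only about 1.03 to 1.14 beyond gestational age; the upper figure of 1.9 should not be read as the gain over the listed model. The shares on support, the BPD risks and the coefficients of the illustrative model are all assumptions. The BPD objective states no time point, so a comparison specifically at 36 weeks should not be read into it.

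**What to change.** For BPD, prespecify:

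1. Adjustment for gestational age and for respiratory support at or immediately before randomisation (for example none, non-invasive, invasive). Take the value from the medical record, not from T0.
2. Removal of ESA use and pRBC transfusion from this model, unless each is restricted to exposure before randomisation.
3. A standardised risk difference with its confidence interval. An adjusted odds ratio alone does not show the precision gain, because adding covariates to a logistic model also changes the odds ratio being estimated.

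The cost is one extra chart value per infant and a little more analysis work. Sample size, study procedures and the primary analysis are unchanged.
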